## 2.4 Rationale for sample size

A total of 300 subjects (150 each for the MT-6548 and darbepoetin groups) should be enrolled in the treatment period.

### [Rationale]

For the primary efficacy endpoint of mean Hb values at treatment period Weeks 20 and 24, the mean Hb value in the darbepoetin group is assumed to be 11.0 g/dL, the difference between the MT-6548 and darbepoetin groups is assumed to be 0 g/dL, and the standard deviation for both is assumed to be 1.73 g/dL. The non-inferiority margin is set at -0.75 g/dL. Calculation of statistical power from these assumptions shows that a sample size of 150 subjects in each group would ensure greater than 95% probability that the mean of mean Hb values in the MT-6548 group and their 95% CI would fall within the target Hb range (10.0–12.0 g/dL) and non-inferiority could be established.

The assumed standard deviation was set at 1.73 g/dL based on the upper limit of the two-sided 95% confidence interval of the standard deviation in the MT-6548 300 mg group at Week 6 in study CI-0022.

## 3. Endpoints

### 3.1 Efficacy endpoints

#### 3.1.1 Secondary endpoints

- (1) Mean Hb values at Weeks 48 and 52 of the treatment period
- (2) Hb values at each evaluation time point in the treatment period
- (3) Proportion of subjects with mean Hb values within the target range (10.0 to <12.0 g/dL), <10.0 g/dL, and ≥12.0 g/dL at each evaluation time point in the treatment period

### 3.1.2 Other endpoints

- (1) Number of days to maintain target Hb values
- (2) Proportion of subjects receiving rescue therapy with ESA formulations, red blood cell transfusion, or phlebotomy
- (3) Study drug dosage
- (4) MT-6548 group only: total number of MT-6548 tablet dosage adjustments
- (5) Iron supplement dosage
- (6) Proportion of subjects receiving oral, intravenous, or (any route) administration of iron supplements
- (7) Proportion of subjects with serum ferritin  $\geq 100$  ng/mL or TSAT  $\geq 20\%$ .
- (8) Changes and rate of changes in iron-related indices (serum iron, TIBC, TSAT, and serum ferritin levels) and hepcidin from the first day of the treatment period
- (9) Changes in hematocrit, red blood cell count, reticulocytes (count and rate), mean corpuscular volume, mean corpuscular hemoglobin, and erythropoietin from the first day of the treatment period
- (10) Changes and rate of changes in systolic blood pressure, diastolic blood pressure, lipids (total cholesterol, LDL-C, HDL-C, LDL-C/HDL-C ratio, triglycerides), and blood glucose from the first day of the treatment period
- (11) QOL indices (EQ-5D-5L, KDQOL)

## 3.2 Safety endpoints

- (1) Adverse events and adverse drug reactions
- (2) Laboratory test values
  - 1) Hematology tests:  
Mean corpuscular volume, mean corpuscular hemoglobin, mean cell hemoglobin concentration, RBC distribution width, WBC count, WBC fractions (neutrophils, eosinophils, monocytes, lymphocytes, basophils), platelet count
  - 2) Blood biochemistry tests:  
Total protein, albumin, blood glucose, urea nitrogen, creatinine, uric acid, CPK, total bilirubin, AST, ALT, ALP, LDH,  $\gamma$ -GTP, Na, K, Cl, Ca, P, Mg, bicarbonate, total cholesterol, LDL-C, HDL-C, triglycerides

- 3) C-reactive protein
- 4) Vascular endothelial growth factor (hereinafter, VEGF)
- 5) Dehydroepiandrosterone sulfate (hereinafter, DHEA-S)
- (3) Resting standard 12-lead ECG
- (4) Dry weight
- (5) Body weight
- (6) Vital signs
- (7) Fundoscopy
- (8) Chest X-ray
- (9) Proportion of subjects with documented Hb values of  $\geq 12.0$  g/dL or  $\geq 13.0$  g/dL
- (10) Proportion of subjects with documented Hb values of  $< 9.0$  g/dL or  $< 8.0$  g/dL.
- (11) Proportion of subjects with a documented Hb increase rate of  $> 0.5$  g/dL/week
- (12) Hb value after dose reduction or interruption of the study drug
- (13) Kt/V

## 4. Definition of Derived Variables

### 4.1 Age at consent acquisition

Age (year) = Date of consent acquisition (year) – Date of birth (year)

However, when (Date of consent acquisition [month] < Date of birth [month]) or (Date of consent acquisition [month] = Date of birth [month] and Date of consent acquisition [days] < Date of birth [days]), 1 is subtracted from the traditional Japanese age system calculated above.

### 4.2 Duration of disease

The duration of disease (year) should be the period from the onset of renal anemia to the consent month and shall be the integer part + 1 digit (rounded). Duration of disease is calculated as follows:

Duration of disease (year) = (Date of consent acquisition [year] – Time of onset [year]) + (Date of consent acquisition [month] – Time of onset [month])/12

If the month of onset is unknown, the month is calculated as 1.

### 4.3 Period from the first day of hemodialysis

The period from the start of hemodialysis (year) should be the period from the start of hemodialysis (time of first hemodialysis or hemodiafiltration) to the month of consent acquisition and should be the integer part + 1 digit (rounded). The period from the start of hemodialysis should be calculated as follows:

Period from the start of hemodialysis (year) = (Date of consent acquisition [year] – Start of hemodialysis [year]) + (Date of consent acquisition [month] – Start of hemodialysis [month])/12

If the month of the start of hemodialysis is unknown, the month should be calculated as 1.

### 4.4 BMI

BMI (kg/m^2) = Dry weight (kg)/(Height [m])

Should be rounded and displayed to one decimal place.

### 4.5 LDL-C/HDL-C ratio

LDL-C/HDL-C ratio = LDL-C (mg/dL)/HDL-C (mg/dL)

Should be rounded and displayed to two decimal places.

### 4.6 Number of days of drug interruptions

The number of days of drug interruptions does not include subject's forgetting to take the drug and is defined by the following formula.

Number of days of drug interruptions (days) = Day of resumption of study drug administration – First day of study drug interruption

If there are multiple interruptions, the sum of them should be used.

Resumption date of study drug administration: After the entry of "Daily Dose" = 0 mg or 0 µg in the CRF, the first dose should be taken when a value of >0 mg is entered for the first time or should be administered when a value of >0 µg is entered for the first time. If the drug interruption continues until Week 52 of the treatment period, days should be calculated based on the visit date after Week 52 of the treatment period as the resumption date. Specifically, if the treatment is completed or discontinued while the drug is interrupted, the day before the day of blood sampling at Week 52 for hematology tests or the day before the day of treatment discontinuation should be used.

First day of study drug interruption: The day of administration when "Daily Dose" = 0 mg or 0 µg is first entered in the CRF.

## 4.7 Study drug administration/treatment duration

For subjects who completed treatment period:

Study drug administration/treatment duration (days) = Day of blood sampling for hematology tests at Week 52 – First day of the treatment period

For subjects who discontinued:

Study drug administration/treatment duration (days) = Day of discontinuation – First day of the treatment period

## 4.8 Study drug administration/number of administration days

The number of days that the study drug is taken (administered) is defined by the following formula.

Number of MT-6548 administration days (days) = Period of study drug administration – Number of days of no study drug administration other than drug interruptions – Number of days of drug interruptions

Number of darbepoetin alfa administration days (days) = Number of doses of darbepoetin alfa once every week  $\times$  7 days + Number of doses of darbepoetin alfa once every 2 weeks  $\times$  14 days + Number of doses of darbepoetin alfa once every 4 weeks  $\times$  28 days

## 4.9 Study drug administration/compliance rate

Drug administration/compliance rate (%) = Number of days of study drug use (administration)/(Period of study drug use [administration] – Number of days of drug interruptions)  $\times$  100

However, if the compliance rate exceeds 100%, it should be 100%.

## 4.10 Mean daily dose/mean weekly dose

Mean daily dose of MT-6548 during each scheduled study visit period\* = Daily dose based on the physician's prescription  $\times$  Period of administration (days)\*3 of the corresponding dose\*2 between the scheduled study visits\*/Period between the scheduled study visits (days)\*4

Mean weekly dose of darbepoetin alfa during each scheduled study visit period\* = Daily dose based on the physician's prescription  $\times$  Period of administration (days)\*5 of the corresponding dose\*2 between the scheduled study visits\*/Period between the scheduled study visits (days)\*4  $\times$  7

\*: For each period between the scheduled study visits, the actual study visit dates will not be considered, and this variable should be fixed as follows:

- ✓ The first day of the treatment period to Week 2 of the treatment period: The first day of the treatment period (Day 1) to 14 days

- ✓ Week 2 of the treatment period to Week 4 of the treatment period: Day 15 to Day 28
- ✓ The same should apply thereafter, and the final period between the scheduled study visits should be Week 48 to Week 52 of the treatment period: Day 337 to the day before the day of blood sampling for hematology tests at Week 52 of the treatment period. However, for subjects who discontinued their treatment, the final period between the scheduled study visits should be up to the day before discontinuation.

\*2: If there are multiple applicable doses, the sum of the calculated values for each dose should be used.

\*3: The number of days without drug administration other than drug interruption should not be excluded from the “period of administration (days).”

\*4: 14 days up to Week 12 of the treatment period and 28 days after Week 12 of the treatment period. However, for subjects who discontinued their treatment, the final period between the scheduled study visits (days) should be the actual number of days until the day before discontinuation.

\*5: “Period from the day of administration of darbepoetin alfa to the day of next administration of darbepoetin alfa.” However, the first treatment period (days) during the scheduled study visit period should be “period from the start date during the scheduled study visit period to the day before the day of the first darbepoetin alfa administration date after the start date during the scheduled study visit period” and the last treatment period (days) should be “from the last day of darbepoetin alfa administration during the scheduled study visit period to the day before the day of the last treatment or the day before discontinuation during the scheduled study visit period.”

The following formula should be used when no darbepoetin alfa is administered during the scheduled study visit period.

Mean weekly dose of darbepoetin alfa = Weekly dose of darbepoetin alfa immediately before the period between scheduled study visits

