#### 4.13 Iron supplement dosage

The dose of iron supplements is defined by the following formula. However, the dose of iron supplements will not be calculated if iron supplements are used as needed.

Mean monthly dose of iron supplements during the screening period\* and each scheduled study visit period\* (tabulation period of iron supplements) = (Daily dose based on the physician’s prescription  $\times$  Period of administration (days) of the corresponding dose during the tabulation period of iron supplements)/Tabulation period of iron supplements (days)  $\times$  30.4375

\*: The number of days of the screening period is “First day of the treatment period – First day of the screening period.”

\*2: For each period between the scheduled study visits, the actual study visit dates are not considered, and this tabulation is fixed as follows:

- ✓ The first day of the treatment period to Week 2 of the treatment period: The first day of the treatment period (Day 1) to Day 14
- ✓ Week 2 of the treatment period to Week 4 of the treatment period: Days 15 to 28
- ✓ The same should apply thereafter, and the final period between the scheduled study visits should be Week 48 to Week 52 of the treatment period: Day 337 to the day before the day of blood sampling for hematology tests at Week 52 of the treatment period. However, for subjects who discontinued their treatment, the final period between the scheduled study visits should be up to the day before discontinuation.

\*3: If there are multiple applicable doses, the sum of the calculated values for each dose should be used.

\*4: For subjects who discontinued their treatment, the final period between the scheduled study visits (days) should be the actual number of days until the day before discontinuation.

\*5: In this tabulation, 1 month is counted as 30.4375 days (365.25/12 = 30.4375).

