## 9) Analysis of the mean dose of the study drug at Week 48 and Week 52 of the treatment period and CRP levels on the first day of the treatment period

For MT-6548 group only, a scatter plot chart should be provided after linear regression with the following variables.

x: Logarithmic CRP value on the first day of the treatment period

y: Mean dose of study drug at Week 48 to Week 52 of the treatment period

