#### **4.10 Mean daily dose/mean weekly dose**

Mean daily dose of MT-6548 during each scheduled study visit period\* = Daily dose based on the physician's prescription × Period of administration (days)\*3 of the corresponding dose\*2 between the scheduled study visits\*/Period between the scheduled study visits (days)\*4

Mean weekly dose of darbepoetin alfa during each scheduled study visit period\* = Daily dose based on the physician's prescription  $\times$  Period of administration (days)\*5 of the corresponding dose\*2 between the scheduled study visits\*/Period between the scheduled study visits (days)\*4  $\times$  7

\*: For each period between the scheduled study visits, the actual study visit dates will not be considered, and this variable should be fixed as follows:

- ✓ The first day of the treatment period to Week 2 of the treatment period: The first day of the treatment period (Day 1) to Day 14
- ✓ Week 2 of the treatment period to Week 4 of the treatment period: Days 15 to 28
- ✓ The same shall apply thereafter, and the final period between the scheduled study visits should be Week 20 to Week 24 of the treatment period: Day 141 to a blood sampling day for hematology tests at Week 24 of the treatment period.

However, for subjects who discontinued their treatment, the final period between the scheduled study visits should be up to the day before discontinuation.

\*: If there are multiple applicable doses, the sum of the calculated values for each dose should be used.

\*: The number of days without drug administration other than drug interruption should not be excluded from the "period of administration (days)."

\*: 14 days up to Week 12 of the treatment period and 28 days after Week 12 of the treatment period. However, for subjects who discontinued their treatment, the final period between the scheduled study visits (days) should be the actual number of days until the day before discontinuation.

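### For MT-6548 completers, SAP 4.10 divides a last interval that ends at the actual sampling date by a fixed 28 days, so visit timing is reported as dose

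*SAP*

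**What the plan says.** The SAP file holds two plans, one for the final data and one for the Phase 1 (Week 24) data. Section 4.10 has the same structure in each. The mean daily dose of MT-6548 in an interval is the prescribed daily dose times the days on that dose within the interval, summed over doses, divided by the days in the interval.

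- **Lead-in to the intervals (both SAPs):** "the actual study visit dates will not be considered, and this variable should be fixed as follows". The intervals that follow are day-number ranges: Day 1 to 14, Day 15 to 28, and so on.
- **Last interval, final SAP:** "Day 337 to the day before the day of blood sampling for hematology tests at Week 52 of the treatment period".
- **Last interval, Phase 1 SAP:** "Day 141 to a blood sampling day for hematology tests at Week 24 of the treatment period".
- **Denominator, note \*4 (both SAPs):** "14 days up to Week 12 of the treatment period and 28 days after Week 12 of the treatment period". Only subjects who discontinued are given their real number of days.

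Two other sections bear on the reading. Section 4.7 of the final SAP computes treatment duration as "Day of blood sampling for hematology tests at Week 52 – First day of the treatment period", which is plainly a subtraction of real dates. Section 4.13 (iron) defines the same intervals but divides by the length of the tabulation period, with no fixed 28.

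**The concern.** For a completer, the number of days in the numerator moves with the date of the last visit and the denominator does not. A late visit then looks like a higher dose and an early visit like a lower one, although nothing about the treatment has changed.

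The last interval is also the one the plan reports by name. In the final SAP, "Mean dose of study drug at Week 48 to Week 52 of the treatment period" is the response variable in the MT-6548 regression on CRP (8.5.2 (3) 9)), and the same quantity is tabulated by facility (8.5.4.4) and by subgroup (8.5.4.5). The Phase 1 SAP uses the Week 20 to 24 equivalent in 8.5.3 (3) 9), 8.5.4.5 and 8.5.4.6. The Phase 1 derivation also returns in the final analysis, because section 8.7 of the final SAP asks for re-tabulation by the Phase 1 method and 8.7.3 includes mean dose at Weeks 20 to 24.

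**Working it through.** **Inputs**

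- Protocol Table 9.1-1, first day = Day 0: Week 24 is Day 168, permitted 161 to 175; Week 52 is Day 364, permitted 357 to 371.
- Both SAPs number the first day as Day 1, so SAP day = table day + 1.
- Last interval starts on Day 141 (Phase 1 SAP) or Day 337 (final SAP).
- Denominator for completers: 28 days.
- MT-6548 dose range: 150 to 600 mg (Protocol 8.3.3).

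**Formulas.** Numerator days = end day − start day + 1. For a constant dose, reported dose = dose × numerator days / 28.

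**The plan's own figure.** The interval just before the last one in the final SAP is Day 309 to 336: 336 − 309 + 1 = 28 days. For a Week 52 visit exactly on schedule (SAP Day 365), the last interval is Day 337 to 364, also 28 days. The stated 28 is therefore reproduced in the final SAP for an on-time visit.

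**Across the permitted window**

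| | Earliest | On schedule | Latest |
|---|---|---|---|
| Final SAP, visit (SAP day) | 358 | 365 | 372 |
| Days from Day 337 to the day before | 21 | 28 | 35 |
| Days / 28 | 0.750 | 1.000 | 1.250 |
| 300 mg reported as | 225 | 300 | 375 |
| 600 mg reported as | 450 | 600 | 750 |
| Phase 1 SAP, visit (SAP day) | 162 | 169 | 176 |
| Days from Day 141 to the visit, inclusive | 22 | 29 | 36 |
| Days / 28 | 0.786 | 1.036 | 1.286 |
| 300 mg reported as | 235.7 | 310.7 | 385.7 |
| 600 mg reported as | 471.4 | 621.4 | 771.4 |

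Each day of visit shift changes the result by 1/28 = 3.6%. In the final SAP, a visit 3 days early or late gives 25/28 = 0.893 or 31/28 = 1.107.

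**Other day numbering.** If the SAP days are read with the first day as Day 0, the final SAP gives 20, 27 and 34 days and the Phase 1 SAP gives 21, 28 and 35. The distortion stays, and the two SAPs still differ by one day for an on-time visit.

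**Group level.** The documents give no distribution of visit dates, so this part rests on assumptions.

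- Symmetric offsets: mean factor 28/28 in the final SAP (no bias) and 29/28 in Phase 1 (+3.6%).
- Spurious SD = offset SD / 28 × dose. For an offset SD of 1, 2 or 3 days this is 3.6%, 7.1% or 10.7%. If every subject took a constant 300 mg, so that the true SD is 0, the table would show an SD of 10.7, 21.4 or 32.1 mg.

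**Check of the remedy.** Dividing by the numerator interval's own length gives 21/21, 28/28 and 35/35, or 22/22, 29/29 and 36/36. A constant dose is then returned unchanged at any visit date.

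**The case against.** The strongest reply is the lead-in, which sets real visit dates aside. If the Week 52 sampling day is taken as nominal, the final SAP's last interval is Day 337 to 364 for everyone, 28 days, and numerator and denominator agree.

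That reading does not carry the text. The last interval abandons day numbers and names a sampling day, which section 4.7 uses as a real date. Nor does it repair both plans. The final SAP stops the day before sampling and the Phase 1 SAP includes the sampling day, so nominal lengths are 28 and 29 days (first day as Day 1) or 27 and 28 (first day as Day 0). A fixed 28 fits only one of them. What stands is that the lead-in and the last interval conflict, and that under a nominal reading the remaining error is one day in 28.

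Other points on that side:

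- **Size.** Visits are meant to fall on the dialysis day after the 2-day gap, which recurs weekly, so many offsets may be zero. This is fair: the window-edge figures are bounds and the offset SDs are assumptions.
- **Iron precedent.** Section 4.13 does not spell out real days for completers. That is true, but its denominator is the interval it defines, with no fixed 28.
- **Importance.** These are descriptive tables and one single-arm regression. That is also true, and it limits the consequence.
- **Cost.** Section 8.5.4.3 of the final SAP says the Phase 1 analysis has been carried out, so a change there is more than an edit to the text.

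**Conclusion.** The concern holds. As written, section 4.10 gives MT-6548 completers a last-interval mean dose that depends on when they came to the visit. Within the permitted window and for a constant dose, the factor runs from 0.75 to 1.25 in the final SAP and from 0.79 to 1.29 in the Phase 1 SAP. The Phase 1 version is 3.6% too high even for an on-time visit, given the SAP's Day 1 numbering. Reported values can leave the protocol's dose range in either direction: 600 mg as 750 or 771 mg, and 150 mg as 112.5 mg (150 × 21/28).

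Subject-level values, SD, minimum, maximum and the means of small facilities are the most exposed. Group means are much less so if offsets are symmetric. Earlier intervals, discontinued subjects, cumulative dosage (4.11), compliance (4.9) and the Hb non-inferiority analysis are not affected.

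Darbepoetin shares the 28-day denominator, but no error is established there. Note \*5 ends its last segment with the phrase "to the day before the day of the last treatment or the day before discontinuation during the scheduled study visit period", which does not fix one end date, and it has a separate rule for intervals without an injection.

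This should be corrected, but it does not touch the trial's main conclusion.

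**What to change.** In section 4.10 of both SAPs:

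1. **Note \*4:** state that for the final interval the denominator is the number of days in the numerator interval, for all subjects including completers. This matches the approach in section 4.13 and the rule already given for discontinued subjects.
2. **Phase 1 interval:** end it the day before the Week 24 sampling, as the final SAP does for Week 52.
3. **Lead-in:** say that it applies to every interval except the last.
4. **Note \*5:** give the last darbepoetin segment the same interval end, so that one definition serves both arms.

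The cost is about two sentences in each SAP and one line of derivation code. If the Phase 1 data are already locked, Protocol 13.4 also requires the reason to be recorded in the SAP and study report, and the revised results to be shown separately from the original plan. The Week 20 to 24 re-tabulation under section 8.7.3 of the final SAP should use the corrected derivation.

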8.3.3 Maintenance dosage and dosage adjustments

(1) MT-6548 Tablet

Maintenance dosage is 150–600 mg once daily and adjusted according to the dosage

adjustment guideline below.

(2) Darbepoetin alfa injection

The maintenance dosage is 5–180 µg per dose once a week, once every 2 weeks, or once every 4 weeks, which will be adjusted as appropriate according to the dosage adjustment guidelines below.

[Dosage adjustment guidelines]

Investigators/subinvestigators will monitor Hb levels throughout the treatment period, and determine whether to adjust study drug dosage or discontinue administration as required. In principle, dosage adjustment will be performed at scheduled visits or on the day of darbepoetin alfa injection; however, an additional visit may be provided for dosage adjustment, if considered necessary, in cases where excessive increases or decreases in Hb levels are of concern based on the Hb time course. In principle, dosage of MT-6548 Tablets and darbepoetin alfa injection will be adjusted simultaneously. If interruption of study drug administration is necessary, administration of MT-6548 Tablets and darbepoetin alfa injection should be discontinued, and if study drug administration is resumed, administration of both drugs should be resumed.

Hb levels will be measured in samples collected in the supine position using a HemoCue® Hb201 DM analyzer; and in principle, these measurements will be used to determine dosage adjustments. Hb levels on the day of dialysis will be measured in samples collected before dialysis. Hb measurements used for dosage adjustment determinations will be recorded in the subject's CRF. Measurement results from the HemoCue® Hb201 DM will be used solely for determination of study drug dosage adjustments, and will not be used for efficacy or safety analysis.

The dosage adjustment algorithm below will be followed in order to maintain Hb levels of 10.0–12.0 g/dL during the study. Dosage steps are defined in the dosage adjustment table below.

MT-6548 Tablet dosage adjustment table

Step	No. of tablets	Dosage
1	1	150 mg or placebo
2	2	300 mg or placebo
3	3	450 mg or placebo
4	4	600 mg or placebo

Darbepoetin alfa injection dosage adjustment table

Step	Dosage
1	5 µg or placebo
2	10 µg or placebo
3	15 µg or placebo
4	20 µg or placebo
5	30 µg or placebo
6	40 µg or placebo
7	50 µg or placebo
8	60 µg or placebo
9	80 µg or placebo
10	100 µg or placebo
11	120 µg or placebo
12	140 µg or placebo
13	160 µg or placebo

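### The end point of the last darbepoetin segment in the mean-weekly-dose rule (SAP 4.10, note *5) is undefined; programmed literally, it gives the last injection no days and understates the comparator dose

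*SAP*

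**What the plan says.** Section 4.10 of the final SAP and of the Phase 1 SAP divides each visit interval into dosing segments for darbepoetin. The wording of note *5 is the same in both.

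- **First segment:** from the start of the interval "to the day before the day of the first darbepoetin alfa administration date after the start date during the scheduled study visit period".
- **Middle segments:** "Period from the day of administration of darbepoetin alfa to the day of next administration of darbepoetin alfa".
- **Last segment:** "from the last day of darbepoetin alfa administration during the scheduled study visit period to the day before the day of the last treatment". With its discontinuation alternative, the end point in full is "to the day before the day of the last treatment or the day before discontinuation during the scheduled study visit period".
- **Interval with no injection:** "Mean weekly dose of darbepoetin alfa = Weekly dose of darbepoetin alfa immediately before the period between scheduled study visits".

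The dose is multiplied by the credited days and divided by a fixed length (note *4): "14 days up to Week 12 of the treatment period and 28 days after Week 12 of the treatment period". Actual days are used only for the final interval of subjects who discontinued.

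Study drug dosage is one of the other efficacy endpoints (Protocol 5.4.1 and 10.1.3). The SAPs summarize it by visit interval, by facility and by subgroup.

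**The concern.** The natural end of the last segment is the last day of the visit interval, for example Day 28 of Days 15 to 28. Note *5 never names that day. Its stated end is the day before the last treatment, and the closing phrase about the scheduled study visit period invites the reader to take this as the last injection in the same interval. The segment would then end one day before it starts. The days from the last injection to the end of the interval would carry no dose but would remain in the denominator.

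At stake is the accuracy of the darbepoetin dose tables and curves, which help a reader of a non-inferiority trial see how the active comparator was dosed. The MT-6548 formula uses note *3 and has no such gap. The loss would vary with the injection schedule. It would also change when visit intervals lengthen from 14 to 28 days after Week 12, so a constant dose could appear to rise at that point.

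**Working it through.** The plan states no figure for this rule, so there is none to reproduce. The check applies the 4.10 formula to a constant dose.

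**Inputs**
- Segment rules: note *5. Interval lengths L = 14 or 28 days: note *4.
- Dose interval τ = 7, 14 or 28 days: Protocol 8.3.3 allows darbepoetin "per dose once a week, once every 2 weeks, or once every 4 weeks".
- Illustrative dose D = 30 µg. The percentages do not depend on it.

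**Assumptions**
- Daily dose = D/τ (4.10 does not say how a daily dose is derived from an injection).
- The first segment is credited at the same ongoing dose.
- Days between injections are counted once.

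**Formula.** Mean weekly dose = (D/τ) × credited days / L × 7. The correct value is 7D/τ, so the reported share is credited days / L.

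**Reading A: last treatment = last injection in the interval.** Credited days run from the interval start to the day before the last injection.

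| L | Schedule | Credited (first injection on first day) | Result vs correct, µg/week | Loss | Mean loss, uniform injection days |
|---|---|---|---|---|---|
| 14 | weekly | 7/14 | 15.0 vs 30.0 | 50% | 4/14 = 28.6% |
| 14 | 2-weekly | 0/14 | 0 vs 15.0 | 100% | 7.5/14 = 53.6% |
| 14 | 4-weekly | 0/14 | 0 vs 7.5 | 100% | 3.75/14 = 26.8% |
| 28 | weekly | 21/28 | 22.5 vs 30.0 | 25% | 4/28 = 14.3% |
| 28 | 2-weekly | 14/28 | 7.5 vs 15.0 | 50% | 7.5/28 = 26.8% |
| 28 | 4-weekly | 0/28 | 0 vs 7.5 | 100% | 14.5/28 = 51.8% |

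The last column is the average number of days lost. For weekly dosing, 1 to 7 days are lost, with mean 4. For 2-weekly dosing the mean is 7.5, and for 4-weekly dosing in 28 days it is 14.5. For 4-weekly dosing in 14 days, half the positions have no injection and lose nothing, so the mean is 7.5/2 = 3.75.

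For weekly dosing on the first day of each interval, an unchanged 30 µg would appear to go from 15.0 to 22.5 µg/week when the interval changes from 14 to 28 days.

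**Reading B: the day before the last day of the interval.** One day is lost: 13/14 (−7.1%) or 27/28 (−3.6%).

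**Reading C: end of treatment, capped to the interval.** 14/14 or 28/28, no loss: 30.0, 15.0 and 7.5 µg/week for the three schedules.

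**Completers' final interval.** In the final SAP this runs from Day 337 to the day before Week 52 sampling. Protocol Table 9.1-1 permits sampling on Days 357 to 371.
- Protocol day numbers as they stand: 356 − 336 = 20 to 370 − 336 = 34 days.
- Allowing for the SAP calling the first day Day 1 where the protocol calls it Day 0: 21 to 35 days.

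Note *4 divides by 28, so even a complete set of segments sums to between 20/28 = 71% and 35/28 = 125% of the denominator. The Phase 1 SAP has the same mismatch, from Day 141 to the actual Week 24 sampling day.

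**The case against.** The strongest reply is that the literal reading was not intended.

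- The note uses one term for the injection and another for the last treatment, and it pairs the latter with discontinuation. Section 4.6 of the final SAP uses a similar pair for the end of treatment: "the day before the day of blood sampling at Week 52 for hematology tests or the day before the day of treatment discontinuation". Section 4.10 likewise ends the final interval the day before Week 52 sampling.
- The formula in 4.10 counts days of a dose between scheduled visits, which already caps segments to the interval. Capped in this way, the end-of-treatment reading gives the correct end. It would therefore be wrong to say that no reading of the words works.
- The literal reading produces an absurdity within the same note. A single injection on the first day of an interval would score zero, while an interval with no injection keeps the previous weekly dose in full.
- The reach is small. The affected outputs are descriptive, and the two arms' doses are in different units. Cumulative dosage (4.11), compliance (4.8 and 4.9), the dose distribution taken from prescriptions, and the hemoglobin analyses do not use note *5.

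All of this stands as to intent and reach. It does not settle the text: the correct result requires the programmer to infer both a meaning and a cap that the note does not state, and two other readings give wrong numbers.

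**Conclusion.** The rule is ambiguous and should be corrected in both SAPs. If programmed literally, mean weekly darbepoetin dose is 25% to 100% too low when an injection falls on the first day of the interval, and about 14% to 54% too low when injection days are assumed uniformly spread. Both ranges rest on a constant dose and the daily-dose convention shown above. The one-day reading loses 3.6% to 7.1%, and the capped end-of-treatment reading loses nothing.

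A reader might infer that the plan does credit the last injection with no days, so that the reported comparator dose is understated in every interval. The documents do not support that. The key term is undefined, a correct reading exists, and the program is not shown. Intervals with no injection follow a separate formula, and the final interval of a subject who discontinued has its own non-empty end point, so neither is affected.

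Nor do the documents support an inference that the non-inferiority result is touched. The reach is limited to descriptive darbepoetin dose summaries, overall, by facility and by subgroup.

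**What to change.** In note *5 of section 4.10 in both SAPs, end the last segment at the last day of the scheduled study visit period, or the day before discontinuation if earlier. State how the daily dose of an injection is derived.

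That change alone does not make the segments sum to the denominator in completers' final interval (from Day 337 in the final SAP, from Day 141 in the Phase 1 SAP). In note *4, use the actual number of days there instead of 28.

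Then check which end point the program used and rerun the dose tables and figures if it differs. The cost is one phrase in each of two notes per SAP, a program check and possibly a rerun. No new data are needed.
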